9 STUDY ASSESSMENTS & PROCEDURES

9.1 ELIGIBILITY CONFIRMATION

At the screening (initial) visit to the lab, Day 0, participants will complete a number of self-report questionnaires to confirm eligibility including self-report health questionnaires and basic demographics.

9.2 VISION TESTING

Participants will undergo a brief vision test that involves standing a set distance from a standard Snellentype eye chart as well as a screening for color-blindness using a common color vision test that involves looking at a circular pattern comprised of many dots of various colors, brightness and sizes.

9.3 PSYCHOLOGICAL ASSESSMENT

Participants will undergo a clinical-administered assessment to identify lifetime and current psychiatric diagnoses, and complete self-report instruments to assess lifetime occurrence and severity of trauma.

- Structured Clinical Interview for DSM-5 (SCID-5-RV) [57]
- Brief Trauma Questionnaire [76]
- Childhood Trauma Questionnaire [77]

9.4 SLEEP ASSESSMENT

We will assess sleep using both objective (actigraphy) and subjective (PSQI) measures to use as compliance indices and covariates. Daily logbooks will supplement these assessments, and are designed to capture wake/bed times, treatment times, etc.

- Wrist actigraphy using the Actigraph Spectrum every day for duration of study
- Daily Logs
- Pittsburgh Sleep Quality Index (PSQI) [95]
- Morning-ness & Eveningness (Owl-Lark) Questionnaire [135]
- Insomnia Severity Index (ISI) [136]

9.5 CLINICIAN-ADMINISTERED* & SELF-REPORTED ASSESSMENTS

We will use validated clinician-rated and self-reported measures of current traumatic stress symptoms. Clinician-administered instruments will be video-recorded and used for fidelity checks by MPI, [name]. We expect to review approximately 20% (random sample) of the recordings.

- *Posttraumatic Stress Disorder Symptom Scale for DSM-5 (PSSI-5) [79]
- PTSD Checklist for DSM-5 (PCL-5) [80]
- *Hamilton Depression Rating Scale (HAM-D) [81]
- *Hamilton Anxiety Rating Scale (HAM-A) [82]
- Depression Anxiety Stress Scale (DASS) [58]
- Beck Scale for Suicidal Ideation (BSSI) [133]
- Work and Social Adjustment Scale (WSAS) [134]

9.6 OTHER SELF-REPORTED ASSESSMENTS

- Demographics/health Information/Student Status forms
- fMRI screening form
- Treatment Expectation & Treatment Satisfaction Questionnaires
- Follow up Questionnaire completed at study completion

9.7 FMRI

Amygdala reactivity will be measured using fMRI and change in BOLD signal measures across the study period. Images will be acquired using an Echo-Planar Imaging sequence (TR=800 ms, FOV=23, slice=2.4mm, 96x96 matrix) to measure brain function at rest and during the EFAT task, optimized to reduce susceptibility artifact. fMRIs (initially at visits 3, 5 and 7 but later changed to only visits 3 and 7) will be scheduled at the North Campus facility and must occur within 7 days of the clinician-administered and self-reported assessments of trauma stress and mood (see Section 9.3)

9.7.1 fMRI Practice

As part of the screening process, individuals will be able to lie in the mock scanner located at the Rachel Upjohn Building. This scanner is built to size, and includes simulating scanner noise from speakers so people can hear the noises associated with scanning.

9.7.2 Resting brain function

Participants are asked to "remain still, keep your eyes open and the fixation mark, let your mind wander freely, but do not fall asleep."

9.7.3 Emotional Face Assessment Task (EFAT)

The EFAT is an effective probe of amygdala reactivity [72] that has been validated in (1) anxious patients [73, 74]; (2) in anxious and healthy participants with pharmacological challenges [73, 75]; and (3) in anxious patients undergoing psychotherapy [74]. Participants will view a trio of faces, and are instructed to match one of the two faces across the top of the screen that expresses the same emotion as the target face shown at the bottom. The target and congruent probe face display one of five expressions (angry, happy, fearful, sad, neutral) and the other (incongruent) probe face always displays a neutral (or happy if the target is neutral) expression. This design isolates amygdala reactivity specifically to different types of cues conveyed by each expression which have similar perceptual characteristics except for the emotional signal. The paradigm consists of 20 face trials per expression and 20 shape trials (each 3 seconds in duration), presented in pseudorandomized order, separated by a 3-7 sec inter-trial 'jitter" (blank screen, fixation cross). During all sessions, our primary measure will be brain response to signals of threat (e.g. fear > happy). Besides fMRI signal, we will also obtain behavioral measures of accuracy and response time to verify participants are following the instructions. To ensure participants understand task instructions, participants will complete practice trials with faces not used in the experiment before undergoing fMRI.

9.7.4 Emotional Regulation Task

The ERT assesses an individual's ability to regulate emotions. The task is designed to elicit positive and negative emotional states; individuals view positive (e.g., flowers), negative (e.g., crying person), and neutral (e.g. fire hydrant) images from a curated repository, the International Affective Picture System. Participants are instructed to regulate their emotional response by either increasing the amount of their emotional response, decreasing it, or simply view the image without any purposeful regulation. The testing paradigm consists of nine iterations of 5 conditions: decrease negative, watch negative, increase positive, watch positive, and watch neutral. The participant's view alternates between a white fixation cross and a picture with the prompt (increase, decrease, or watch) superimposed. During this time the participant tries to regulate their emotion as instructed. Between each trial participants are asked to rate the intensity of the emotion they experienced.

9.8 Treatment expectation & Treatment Satisfaction

Prior to the start of their morning light treatment, participants will rate their expectations for treatment on a 0-10 numerical rating scale (0 "do not expect to benefit" to 10 "expect to benefit a lot"). Participants will then rate their level of satisfaction with their treatment at the final study visit.

9.9 OTHER RESEARCH PROCEDURES

9.9.1 Urine drug/pregnancy screen

All female participants of childbearing age take a urine pregnancy test at visit 1, visit 5, and every visit with an fMRI; additionally, we will also do a dip stick drug screen to assess for illicit drug use on all participants during lab Visits 1, 2, 5, and at every visit with an fMRI.

9.9.2 Breathalyzer

Participants will be evaluated for recent alcohol use at each study visit by blowing into a breathalyzer.

9.9.3 Self-reported medical history

Participants will fill out a comprehensive medical history and current medications.

9.10 SAFETY ASSESSMENTS

9.10.1 SAFTEE for treatment side effects

An unblinded study team member will administer the SAFTEE (Systematic Assessment for Treatment Emergent Events) at weekly study visits.

If a participant reports a significant worsening of symptoms as indicated by a score of 4 ("bothered quite a bit") or 5 ("bothered extremely"), or endorses any of the following trigger points, the study team will contact [name] as soon as possible who will then contact the participant for additional information. Decisions on subsequent actions (e.g. withdrawal, referral to treatment, etc.) will be made by the MPIs who may decide to withdraw the participant from the study, and refer them to appropriate treatment.

Trigger Point Items from the SAFTEE

- Loss of consciousness (2 or more)
- Seizures (2 or more)
- Difficulty swallowing (3 or more)
- Chest pain (2 or more)
- Shortness of breath (2 or more)
- Rapid heart rate (2 or more)
- Irregular heart beat (2 or more)
- Feeling restless or like you cannot stay still (3 or more)
- Too much energy (3 or more)
- Jumpiness or feeling jittery (3 or more)
- Feeling excited (3 or more)
- Overactive (3 or more)
- Elated (3 or more)

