8 END-OF-INTERVENTION/END-OF-STUDY

8.1 DISCONTINUATION OF INTERVENTION

Use of the Re-Timer will be stopped in the event of:

- Significant clinical deterioration or expressed suicidal ideation at the determination of the study team
- Severe treatment side effects at the determination of the study team
- Significant decline in physical health making compliance with the intervention either ill-advised or challenging to complete
- Participant request to discontinue therapy

Reasons for discontinuation will be documented, and all outcome assessments will proceed as scheduled, if possible.

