8.2 Participant Discontinuation or Withdrawal from Study

Reasons why a participant might be withdrawn from the study:

- Participant request
- Any new diagnosis that would be considered part of the original exclusion criteria for this study
- Positive breathalyzer or drug test at the study at Visits 3, 4, 5 or 6
- Start of new treatment or therapy during study period
- Significant study intervention non-compliance, i.e. inability or unwillingness to complete study intervention or outcome assessments
- Any clinical event or other medical condition or situation such that continued participation in the study would not be in the best interest of the subject
- If the participant meets an exclusion criterion (either newly developed or not previously recognized) any time
- Lost-to-follow up

If possible, reasons for withdrawal will be documented. Data from dropouts or withdraws will be retained to minimize data loss.

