11 STATISTICAL CONSIDERATIONS

11.1 GENERAL APPROACH

The objective of this study is to establish a signification dose response relationship between the duration of morning light treatment and reduction in amygdala reactivity from baseline to treatment week 2 (study week 3) and/or treatment week 4 (study week 5).

Statistical analyses will include intent-to-treat and completer analysis. Data will be analyzed using responses at all three times (baseline, 2 [when data available] and 4 weeks) as dependent variables using a mixed-effects longitudinal model [106, 107] with participants as random intercepts to account for between participant variability and time as a predictor.

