11.1.2 Go/No-go Criteria

A meaningful reduction in amygdala reactivity (Cohen's d≥0.5) must be observed with one of the three daily light durations at treatment week 2 and/or treatment week 4.

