12.3 SAFETY OVERSIGHT

12.3.1 Clinical Monitoring

The clinical status of participants is monitored throughout the study. Any >25% worsening from baseline measures of depression and anxiety are flagged for review by the MPIs. Any >50% worsening of these measures is grounds for discontinuing the participant, with careful follow up (no participant in our pilot study worsened to this degree).

- MPI, [name] is the study expert in PTSD and traumatic stress. She will have weekly clinical coordinating meetings with Co-Is [name] and [name] regarding the clinician-administered assessments, and review the self-report instruments as needed. She, and [name] and [name], will be available to consult on all noted psychological events. Any indication of clinical worsening or suicidal ideation will be managed in real-time before the participant leaves the lab. In cases where additional treatment is recommended or indicated, appropriate referrals or transport to UM Psychiatric Emergency Department will be provided.
- Co-I, [name], will be available to consult on all medical matters and SAFTEE reports. As with instances of worsening psychological status, treatment referrals and communication with personal physicians will be provided as needed.
- Co-Is [name] and [name] will be available to consult on abnormal fMRI findings. Any incidental findings will be discussed with the participant and their personal physician with referrals made as needed.
- Adjudication on whether to withdraw a participant from the study because of change in clinical status will be the purview of the MPIs and Co-Is.

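### Safety withdrawals before Visit 7 leave no post-baseline scan; the protocol does not say whether Section 8.1 governs them, and missing-data work is conditional and not tied to the Go rule

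*Combined protocol and SAP*

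**What the plan says.** **Scans.** Section 9.7 records that fMRI was "initially at visits 3, 5 and 7 but later changed to only visits 3 and 7". The Section 1.3 schedule agrees and describes no early-exit scan.

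**Leaving after harm.**
- Section 9.10.1, on SAFTEE triggers: "Decisions on subsequent actions (e.g. withdrawal, referral to treatment, etc.) will be made by the MPIs who may decide to withdraw the participant".
- Section 12.3.1 makes worsening of more than 50% in depression or anxiety "grounds for discontinuing the participant, with careful follow up (no participant in our pilot study worsened to this degree". It adds a separate step: "Adjudication on whether to withdraw a participant from the study because of change in clinical status" lies with the MPIs and Co-Is.
- Section 8.2 lists possible reasons for study withdrawal. One is "Start of new treatment or therapy during study period". Another is a general best-interest clause. Data already collected are kept.

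**Stopping the light only.** Section 8.1 covers severe side effects and significant clinical deterioration by stopping the device: "Reasons for discontinuation will be documented, and all outcome assessments will proceed as scheduled, if possible".

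**Analysis.** Section 11.1 plans both intent-to-treat and completer analyses, using "responses at all three times (baseline, 2 [when data available] and 4 weeks) as dependent variables" in a random-intercept model. Section 11.2 names pattern-mixture and selection models for the key outcomes, but only if non-ignorable missingness is detected. Under Section 11.1.2 a reduction of Cohen's d≥0.5 "must be observed with one of the three daily light durations at treatment week 2 and/or treatment week 4". That section names no analysis set, standardiser or missing-data rule.

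**The concern.** Two people with the same safety event can be treated differently. One stops light under 8.1 and is still scanned at Visit 7. The other is withdrawn under 9.10.1 or 12.3.1 and contributes only a baseline scan. The choice is discretionary, and the text sets no default.

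The Go result decides the move to the next phase (Section 4). If those who leave would have shown poorer amygdala change, each arm's remaining participants look better than the arm as randomised, whatever the dose pattern of exits. Section 2.1.1 links amygdala hyperactivity to PTSD, depression and anxiety symptoms. That makes the assumption plausible for exits due to worsening, but not for the somatic or elation triggers.

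The safeguard in 11.2 may never operate. Whether missingness depends on the unseen value cannot be settled from the values that were seen, so a condition that it be detected is not a usable trigger. Intent-to-treat keeps a baseline-only participant in the mixed model under a missing-at-random assumption, but it cannot supply that person's unobserved change.

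**Working it through.** The protocol gives no exit rate, alpha, power or SD, so there is no planned figure to reproduce. What follows is an illustration.

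**Inputs.** From the documents: 66 participants (Section 6), three arms (7.4.1), and d≥0.5 in any one arm (11.1.2). Assumed: an equal split, 66/3 = 22 per arm; no true effect; d = mean change / SD of change; one follow-up time; exit rates; and a correlation of 0.3-0.7 between the tendency to exit and amygdala change.

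**1. No exits.** One arm reaches d≥0.5 with probability P(t with 21 df ≥ 0.5×√22 = 2.345) = 0.0145. For any of three arms: 1 − (1 − 0.0145)³ = 4.3%.

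**2. Exits related to change (simulation).** Change is standard normal, and a participant exits if a correlated liability falls in the top fraction p of the arm.

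| Exits at 15/30/60 min | Exits unrelated to change (smaller n only) | Exits related to change |
|---|---|---|
| 1/2/5% | 4.6% | about 5.6-7.4% |
| 2/5/10% | 5.1% | about 7.5-12.4% |

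Selection itself therefore adds 5.6 − 4.6 = 1.0 to 7.4 − 4.6 = 2.8 points in the first row, and 2.4 to 7.3 points in the second. Expected scans lost are 22×0.08 = 1.8 and 22×0.17 = 3.7.

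**3. Dose slope.** Favourable false positives in a random-intercept model (nominal 2.5%) are 2.8-3.2% at 1/2/5% and 2.9-4.0% at 2/5/10%. When exits fall with dose (20/10/5%) they are 0.6-1.8%. The bias is small, and its sign depends on which arm loses people.

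**4. How fragile is an observed d of 0.50?** Take m completers with mean reduction 0.5 and SD 1, and k = 22 − m missing whose mean is a worsening of δ.
- Mean = (0.5m − kδ)/22.
- SD² = [(m − 1) + k + (mk/22)(0.5 + δ)²]/21. The term k is the spread among the missing. Filling in one constant value drops it.
- Example, k = 4 and δ = 0: mean = 9/22 = 0.409; SD² = (17 + 4 + 0.818)/21 = 1.039; d = 0.401. A constant fill gives SD² = 17.818/21 = 0.848 and d = 0.444.

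| Missing of 22 | δ = 0 | δ = 0.5 | δ = 1 |
|---|---|---|---|
| 1, spread kept | 0.475 | 0.445 | 0.411 |
| 1, constant fill | 0.486 | 0.455 | 0.420 |
| 4, spread kept | 0.401 | 0.296 | 0.196 |
| 4, constant fill | 0.444 | 0.324 | 0.211 |

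One missing scan can reverse a borderline Go. Constant filling makes Go look sturdier than it is.

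**5. Does keeping scans help?** At 2/5/10% and correlation 0.5, the chance of a Go is 9.4%. If 80% of those who exit are still scanned, it is 5.1%. This assumes the retained scans are not altered by rescue drugs.

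**The case against.** **Section 8.1 already names severe side effects and deterioration.** It does, and 8.2 names neither. 9.10.1 is permissive, and 12.3.1 pairs discontinuing with follow-up. The likeliest reading is 8.1 by default and withdrawal by exception. A reader might infer that every safety event costs a scan, or that starting a new treatment is itself an exit for harm. The documents support neither. What stands is that no sentence makes 8.1 the default.

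**Missing data are addressed.** A reader might infer that the plan has no provision. It plans intent-to-treat and completer analyses, and the key outcomes in 11.2 plausibly include amygdala reactivity. What stands is that the trigger is unusable and that nothing links these analyses to Go.

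**Exits are rare.** Sections 2.1.2 and 3.1.4 say side effects rarely lead to stopping, and 12.3.1 reports no pilot participant worsening by more than 50%. The lower rates are therefore the more likely ones. If that pilot is the n=13 trial in 2.1.2, none of 13 still allows up to 1 − 0.05^(1/13) = 20.6% (one-sided 95%), but for that degree of worsening only. Exits of 5/10/20% with correlation 0.7 would give about 27%. A reader might take that as the expected size, but the documents do not suggest such rates.

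**The standardiser is undefined.** This stands. Scaling by baseline SD instead gives a no-exit figure of about 8.8% or 2.4% at baseline/follow-up correlations of 0.3 or 0.6, a swing larger than the effect at 1/2/5%.

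**Other sources.** The Data and Safety Monitoring Plan and the wider R61/R33 proposal were not supplied and may hold relevant rules. Some participants scanned under the earlier schedule may have a Visit 5 scan.

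**Conclusion.** The point holds as a recommended, not a critical, change. Study withdrawal before Visit 7 removes the only post-baseline scan under the current schedule. The choice between the 8.1 rule and withdrawal is unstated for overlapping safety events. The missing-data step rests on a condition that cannot be verified and is not attached to the Go decision in this document.

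The likely size is modest: a few percentage points on the chance of a false Go, part of it from smaller n alone. It depends on the assumed link between exit and amygdala change, the assumed exit rates, 22 per arm, and scaling by the SD of change. A reader might infer that the dose-response test is biased in the treatment's favour. The documents do not support that, because exits could concentrate in any arm.

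**What to change.** 1. **Sections 8.2, 9.10.1 and 12.3.1.** State that safety exits follow 8.1 by default: stop the light, but still seek the planned Visit 7 scan and ratings where safe and with consent, never delaying care. Sections 6.2 and 7.6 bar SSRIs, SNRIs, benzodiazepines, beta blockers and opioids because they can dampen amygdala reactivity, so a scan after such a rescue drug could count a drug effect as a light effect. Report the Go effect size with and without scans taken after one is started, treating those scans as missing in the second version.
2. **Section 11.2.** Delete the condition on detection. Always run a delta-adjusted multiple-imputation tipping-point analysis over everyone randomised, for both the dose-by-time term and the Go effect size. Let the mean change assigned to those without a Visit 7 scan run from none to 1 SD of worsening, keep the residual variance, and report where the Go result reverses.
3. **Reporting.** Tabulate safety exits and missing Visit 7 scans by arm and reason, or cite the Data and Safety Monitoring Plan if it already does so.

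**Cost.** Wording in the sections named, one sensitivity analysis and one small table. There is no new visit: about 2 to 4 already planned scans are at stake at exits of 1/2/5% to 2/5/10%. Some retained scans will reflect light plus rescue treatment, some people will decline, and the Go result may look slightly less favourable.

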9.10.2 Columbia Suicide Severity Rating Scale (C-SSRS)

The C-SSRS is used widely in a variety of clinical and research settings, and is sensitive to change over time [97, 132]. All instrument administrators will complete the required online clinical trials training module provided by the developers of the measure prior to administering the instrument. Updated training is required every 2 years. Study staff will review the C-SSRS before the participant leaves the session. If a participant reports significant suicidality at any point during the study (C-SSRS item 4 or 5 = yes), Co-I, [name] (a specialist in suicide), will review the intensity of ideation score (range = 2-25) and speak with the participant to discuss the participant's symptoms and conduct an evaluation before the participant leaves the study session.

10 ADVERSE EVENTS

The Data and Safety Monitoring Plan is the definitive source for this study's strategy for upholding data integrity and participant safety. Briefly, this study is considered "minimal risk" because the probability and magnitude of harm or discomfort anticipated in the research are not greater than those normally encountered in daily life or during the performance of routine medical and psychological care. Safety of subjects will be ensured by the continued monitoring of their mental health and medical status. Participants will all have access to treatment-as-usual services to address any clinical concerns or study-induced adverse effects.

This study will use an independent safety monitor with experience in conducting clinical trials for psychiatric disorders, fMRI, biostatistics, and human subjects protections and research ethics. NIMH will approve the safety monitor prior to initial of the study.

10.1 DEFINITIONS

An adverse event (AE) is any unfavorable or unintended symptom, sign, or disease associated with a medical treatment or procedure that may or may not be related to the treatment or procedure. Adverse events can be related to the treatment or to the disorder being treated (e.g. clinical worsening), as well as to a concurrent disorder or treatment (e.g. depression or its treatment), or they could be entirely unrelated to any of these (e.g., motor vehicle accident).

